8.2 Blinding

Due to the objectives of the study, the identity of test and control treatments will not be known to investigators, research staff, or patients. The following study procedures will be in place to ensure double-blind administration of study treatments:

- Access to the randomization code will be strictly controlled.
- Packaging and labeling of test and control treatments will be identical to maintain the blind.
- Due to necessity of evaluate the activity of treatment product, both packages(with different letters) will be sent to microbiology lab to determine the activity of strains, the result will be blind without mention to any letter.
- Full blinding is done after the last participant of the intervention is done. The investigator will send an email to the company asking for unblinding.

The study blind will be broken on completion of the clinical study and after the study database has been locked. Investigators will be made aware of their subjects treatment assignments after all participant finish the treatment duration, three months.

During the study, the blind may be broken **only** in emergencies when knowledge of the patient's treatment group is necessary for further patient management. When possible, the Investigator should discuss the emergency with the Medical Monitor prior to unblinding.

For blinding in emergency case, the investigator has 2 options:

1. Have direct contact with the company (mobile) personnel in charge of blinding (preferrable)
2. Assign a 3rd individual not included in the team to whom the company will share the blinding information.

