8 STUDY TREATMENTS

8.1 Method of Assigning Subjects to Treatment Groups

In allocation process, a randomization center will be involved in randomizing the participants in two groups, also there will be allocation concealment, according to the following steps:

- Hexbio company will provide sachets which only have alphabet Q or R.

- In the beginning of the study, participants will be given a unique number by the research phlebotomist.
- The randomization scheme will be computer generated in which all participants will be allocated (1:1) in two different groups, group Q and group R.
- After completing the intervention, a request letter will be sent to the company in order to unblind the study.
- Then the company lab will send an unblinding letter to inform us which alphabet is probiotic or placebo.

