9.3 Pharmacokinetic Measurements

All analyses will be done in the CBCD, KSU using colorimetric method. Regular blood analysis will be taken at baseline and at the end of the study, then are kept into plan red covered tubes. All blood samples will be centrifuged (3500×5 mins) to separate serum samples. All tubes should be placed vertically for 45 minutes until the sample is completely coagulated, then transported to CBCD, KSU for further analysis.

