16 DATA COLLECTION, RETENTION AND MONITORING

16.1 Data Collection Instruments

The Investigator will prepare and maintain adequate and accurate source documents designed to record all observations and other pertinent data for each subject treated with the study drug.

Study personnel at each site will enter data from source documents corresponding to a subject's visit into the protocol-specific electronic, Case Report Form (eCRF) and paper CRF when the information corresponding to that visit is available. Subjects will not be identified by name in the study documents to be collected by the Sponsor (or designee) but will be identified by a subject number.

For eCRFs: If a correction is required for an eCRF, the time and date stamps track the person entering or updating eCRF data and creates an electronic audit trail. For paper CRFs: If a correction is made on a CRF, the study staff member will line through the incorrect data, write in the correct data and initial and date the change.

The Investigator is responsible for all information collected on subjects enrolled in this study. All data collected during the course of this study must be reviewed and verified for completeness and accuracy by the Investigator

Data Management Procedures

The data will be kept in paper documents and e-documents, the study doesn't have database.

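### Unblinding waits for a database lock (8.2), but the study has no database (16.1), and other statements in 8.1 and 8.2 let the Q/R key be released once treatment ends

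*Combined protocol and SAP*

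**What the plan says.** Four places in the protocol govern when the treatment code is opened.

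- Section 8.2 gives the only condition that refers to data: "The study blind will be broken on completion of the clinical study and after the study database has been locked".
- Section 8.1 sets the request to the manufacturer: "After completing the intervention, a request letter will be sent to the company in order to unblind the study". The reply follows: "Then the company lab will send an unblinding letter to inform us which alphabet is probiotic or placebo".
- A bullet in 8.2 reads: "Full blinding is done after the last participant of the intervention is done". The sentence after it, "The investigator will send an email to the company asking for unblinding", shows that unblinding is meant.
- Section 8.2 then sets disclosure: "Investigators will be made aware of their subjects treatment assignments after all participant finish the treatment duration, three months".

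On data handling, section 16.1 describes an eCRF with time stamps and an audit trail, paper CRFs with initialled corrections, and a duty on the investigator to verify all data. Under Data Management Procedures it then says: "The data will be kept in paper documents and e-documents, the study doesn't have database". Section 16.2, on data quality control, is marked as not applicable.

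**The concern.** The plan's one data safeguard on unblinding refers to something that the plan says does not exist. Staff looking for the moment at which they may ask for the key would find three other statements, each satisfied when the last participant finishes three months of treatment. They could follow 8.1 exactly and learn the active letter while records are still being checked and samples assayed.

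What is at stake is who knows the arm when judgement is still being used. Corrections to Visit 2 records, the handling of protocol violations and the choice of who is analysed should all be settled first. The audit trail and initialled corrections would record later changes to the data but not prevent them, and they do not cover decisions about the analysis set.

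**Working it through.** The documents give no figure to reproduce, so the check is mainly textual.

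**Step 1. Conditions side by side.**

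| Place | Event | Earliest time | Condition on the data |
|---|---|---|---|
| 8.1 | Request letter to the company | Intervention completed | None |
| 8.2, bullet | Email to the company | Last participant done | None |
| 8.2, lock sentence | Blind broken | Study completed | Database locked |
| 8.2, next sentence | Investigators told assignments | All have finished three months | None |

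**Step 2. Can the single data condition operate?** It needs a database, and 16.1 says there is none. No lock, freeze or sign-off of the eCRF, the paper CRFs or an analysis file appears elsewhere. The only other locked items are file cabinets (16.3 and 17), which concern storage. Section 15.5 places all analysis at the end of the intervention and adds no cleaning interval.

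**Step 3. What is still open when treatment ends?**

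- Blood is collected at Visit 2 (10.2). Samples are separated, "then transported to CBCD, KSU for further analysis" (9.3).
- Diaries and returned sachets are brought back and reviewed at Visit 2 (8.7, Appendix 1).
- The investigator's verification of all data (16.1) has no date relative to unblinding.
- Section 15 includes all patients by intention to treat, while 15.1 includes all eligible subjects. Section 13 leaves it to the sponsor whether a violation leads to withdrawal.

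**Step 4. How much does one letter reveal?** Participants are allocated 1:1 to Q or R, 45 + 45 = 90. Naming the active letter reveals all 90 assignments at once.

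**Step 5. Scale, by assumption only.** The documents give no SD and no share of contestable decisions. Suppose a fraction q of participants have contestable inclusion, there is no treatment effect, changes in WC are normal with mean zero, and every contestable call is made by result in favour of the probiotic. Half of the contestable participants in each arm are then dropped. The shift in the difference, in SDs of change, is 2 × 0.399q / (1 − q/2). The standard error with 45 per arm is √(2/45) = 0.211 SD.

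| q (assumed) | Expected number dropped, 90 × q/2 | Shift (SD of change) | Shift / SE |
|---|---|---|---|
| 5% | 2.25 | 0.0399/0.975 = 0.041 | 0.2 |
| 10% | 4.5 | 0.0798/0.95 = 0.084 | 0.4 |
| 20% | 9 | 0.1596/0.90 = 0.177 | 0.8 |

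For each assumed q this is an upper bound, because every contestable call goes one way. It is not an estimate for this trial.

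**The case against.** The strongest reply is that the lock sentence governs. The other three statements give earliest times, and an earliest time does not contradict a later condition. Completion of the study can operate as a condition of its own and may be meant to include Visit 2 and its assays. Section 16.1 describes an eCRF, so something lockable exists, and the remark about a database may mean only that there is no dedicated system. On that view the defect is a wrong noun.

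Much of this stands: the intention to lock first is explicit. But completion of the study describes study status, not the state of the data. It is also loosely defined: the synopsis lists three months of follow-up, while 4.1 gives three months' participation in all. If the eCRF is meant, no step to freeze it is given and the paper CRFs are left out. A reader of 8.1 alone is not told to wait for anything.

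Stronger readings are tempting, and the documents do not support them:

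- *That WC would be measured with the arm known.* Anthropometry belongs to Visit 2, at the end of the three months (10.2). The pending assays are LPS, liver enzymes, antioxidant enzymes, HbA1c and lipids (9.2.2).
- *That the laboratory would be unblinded.* Section 17 identifies specimens by coded number and initials only.
- *That eligibility will be reopened after treatment.* Section 4.1 settles it at screening, so 15.1 can be read as the enrolled set. The three-month weight question in 10.1 is a medical-history item and does not compete with the one-month criterion in 6.2.
- *That a known bias or false-positive rate follows.* Every input to Step 5 is assumed. Selecting by result under masked Q/R labels would also raise false positives; early release of the key adds a direction.

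**Conclusion.** The concern holds in limited form. The only data condition on unblinding cannot operate as written, and the remaining statements permit the key to be requested or disclosed once treatment ends. Corrections and analysis-set decisions could therefore be made with the active arm known. This rests on a literal reading of 8.1, 8.2 and 16.1, and on no lock procedure existing outside the document.

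The size of any bias cannot be calculated from the documents, and nothing in them shows that such decisions are likely. The assumed range in Step 5 (0.04 to 0.18 SD of change, or 0.2 to 0.8 standard errors) says only that the exposure need not be trivial. The point should be corrected before the key is requested. It does not call the randomisation, the blinding during treatment or the measurement of WC into question.

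**What to change.** In 8.2, replace the reference to a locked database with a dated, signed freeze of the CRF/eCRF analysis file. The freeze should follow verification of all Visit 2 entries, receipt of all laboratory results and a written record of analysis-set decisions. Make the request letter in 8.1, and the email and disclosure statements in 8.2, conditional on that freeze. Under Data Management Procedures in 16.1, name the file that is to be frozen.

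The cost is a few sentences in three sections. The unblinding letter waits for the last laboratory results and CRF checks. No participants, visits or assays are added, and emergency unblinding under 8.2 is unchanged.

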8.3 Formulation of Test and Control Products

Company's name: B-CROBES LABORATORY SDN. BHD.

Product : HEXBIO[®] MCP[®] Granule (Original Flavour)

Generic Name : MCP[®] BCMC[®] strains

Trade Name : HEXBIO[®]

8.3.1 Formulation of Test Product

HEXBIO[®] is a cream-coloured, original flavoured granular powder containing 6 microorganism strains. The microorganisms / active ingredients in HEXBIO[®] are; *Lactobacillus acidophilus* BCMC[®]12130, *Lactobacillus casei* subsp BCMC[®]12313, *Lactobacillus lactis* BCMC[®]12451, *Bifidobacterium bifidum* BCMC[®]02290, *Bifidobacterium infantis* BCMC[®]02129, and *Bifidobacterium longum* BCMC[®]02120.

Table X: Formulation and Measured pH of XXX and Placebo

	Hexbio	Placebo
Active Ingredient, mg/mL	Lactobacillus acidophilus BCMC [®] 12130, 107 mg Lactobacillus casei subsp BCMC [®] 12313, 107 mg Lactobacillus lactis BCMC [®] 12451, 107 mg Bifidobacterium bifidum BCMC [®] 02290, 107 mg Bifidobacterium infantis BCMC [®] 02129, 107 mg Bifidobacterium longum BCMC [®] 02120. 107 mg	excipients, i.e., maize starch and maltodextrins 3 g

8.3.2 Formulation of Control Product

A placebo containing similar granule appearance as the treatment without 6 probiotic strains will be provided by the Sponsor in a plain box containing 6 zipper bags (10 sachets in each zipper bag). Each sachet is for single use and ready for administration.

8.3.3 Packaging and Labeling

Packaging: Study drug is supplied in cartons containing 1,200 single use sachets. The sachets will be packaged in sets of 10 enclosed within a transparent zipper bag. Six zipper bags will be contained in one plain box labeled with instruction for use and storage. Twenty plain boxes will be contained in each carton.

Labeling: Each **plain box of study drug (not carton)** will be labeled with the required FDA warning statement, the protocol number, a treatment number, the name of the sponsors, and directions for patient use and storage. Each sachet will be labeled with OA-R-01 or OA-Q-01 and Expiry date.

8.4 Supply of Study Drug at the Site

The Sponsor will ship the supplementation after all required regulatory documentation has been received by the Sponsor and a contract has been executed.

8.4.1 Dosage/Dosage Regimen

B-CROBES LABORATORY SDN. BHD. (588778-K) [name]. Contact Number: [contact]		OA-R-01
Study no.		
Treatment no.		
Dosage form	3g of granules per sachet	
Instructions for Use	1 sachet to be taken twice daily. Can be taken before or after meal. Drink a glass of water.	
Route of Administration	Oral	
Storage Conditions	Storage below 25°C. Protect from sunlight and moisture.	
Pack size	60 sachets per box	
Expiry Date		
NOT FOR SALE. KEEP OUT OF REACH OF CHILDREN		

8.4.2 Dispensing

Investigator will dispense the product at study site.

8.4.3 Administration Instructions

One sachet to be taken orally twice daily. Before or after meal, pour one sachet directly into the mouth. Drink a glass of water.

8.5 Supply of Study Drug at the Site

Once the sponsor received the written request from the investigator, the sponsor will arrange the production of study drug which takes 1-2 months. The investigator will need to send a written notice and request for additional study drug if it is necessary in advance so the sponsor will arrange for production accordingly.

8.5.1 Storage

Study drug should be stored by the study site at room temperature below 25°C with air conditioning. If the temperature of study drug storage in the clinic/pharmacy exceeds 25°C, this should be reported to the Sponsor or designee and captured as a deviation. Subjects will be instructed to store the medication in original packaging (plain box and protected from sunlight) at room temperature below 25°C according to the instructions outlined on the Drug Administration Instructions.

8.6 Study Drug Accountability

An accurate and current accounting of the dispensing and return of study supplement for each subject if there is any side effect. All those details will be recorded by a member of the study site staff. The study monitor will verify these documents specially in the first week of the intervention.

8.7 Measures of Treatment Compliance

Subjects will be asked to keep a participant's diary noting the day and date they take their study probiotic supplement and any adverse events. They will be asked to bring their diary to next study visit along with all used and unused probiotic or placebo sachets.

9 STUDY PROCEDURES AND GUIDELINES

A Schedule of Events representing the required testing procedures to be performed for the duration of the study is diagrammed in Appendix 1.

Prior to conducting any study-related activities, written informed consent and the Health Insurance Portability must be signed and dated by the subject.

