5 CRITERIA FOR EVALUATION

5.1 Primary Efficacy Endpoint

The primary outcome is the relative change in WC measurement from baseline to end-of-treatment.

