10 EVALUATIONS BY VISIT

10.1 Visit 1 in the beginning of study:

1. Review the study with the subject and obtain written informed consent.
2. Assign the subject a unique screening number.
3. Record demographics data.
4. Record medical history, including:
 - Stability of weight in the last three months prior the study.
 - Having any of the following diseases: Thyroid disorders, Diabetes type-1, Diabetes type-2, (Any type of disease) Cancer, Neurological disorders, psychiatric disorders, or other.
 - Having any of weight loss surgeries.
 - Enrolling in any diet during the past three weeks.
 - Taking antibiotics in the past 3 weeks.
 - Taking any probiotic supplements regularly for the past 3 months.
 - For ladies:
 - Are you planning to become pregnant in the next three months?
 - Are you taking any hormonal therapy?
5. Perform a complete physical examination.
6. Explain the possible side effect.
7. Perform and record results of blood pressure testing.
8. Collect blood for clinical laboratory.
9. Allocation process which includes randomizing the participants in two groups and allocation concealment.
10. Taking food frequency record for probiotics & prebiotics.
11. Taking 24-hour record.

12. Taking anthropometric measurements.
13. Taking physical activities.

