10.2 Visit 2 at the end of the study (3 months length)

1. Perform an abbreviated physical examination
2. Perform and record results of blood pressure testing.
3. Collect blood for clinical laboratory.
4. Taking 24-hour record
5. Taking anthropometric measurements.
6. Taking physical activities.

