10.3 Early Withdrawal Visit

1. Record any Adverse Experiences and/or review subject diary for adverse experiences and exclusionary medication use.
2. Record changes to concomitant medications.
3. Perform complete physical examination.
4. Perform and record vital signs.

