12.3 Withdrawal of Subjects from the Study

A subject may be withdrawn from the study at any time if the subject, the investigator, or the Sponsor feels that it is not in the subject's best interest to continue.

All subjects are free to withdraw from participation at any time, for any reason, specified or unspecified, and without prejudice.

Reasonable attempts will be made by the investigator to provide a reason for subject withdrawals. The reason for the subject's withdrawal from the study will be specified in the subject's source documents. As noted above, subjects who discontinue study treatment early (i.e., they withdraw prior to Visit 2) can have an early discontinuation visit.

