15 STATISTICAL METHODS AND CONSIDERATIONS

The primary outcome of this study is the difference in waist circumference between groups after 12 weeks of supplementation. The analysis of this study will include all the patients using intention to treat (ITT) methodology. Waist circumference of two groups after 12 weeks of supplementation will be examined for statistical significant using repeated measures ANOVA.

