APPENDIX 1. EXAMPLE OF SCHEDULE OF STUDY VISITS

	VISIT 1 (Day/Week/Month #) ^a	VISIT 2 (Day/Week/Month #) ^a
Informed Consent	X	
Medical History	X	
Complete Physical Exam	X	
Abbreviated Physical Exam		X
Height	X	X
Weight	X	X
Vital Signs	X	X
Oximetry		
Spirometry		
Pharmacokinetics		X
Chemistry	X	X
Pregnancy Test (Urine or Serum)		
Hematology		
ESR		
C-Reactive Protein		
Urinalysis		
Randomization	X	
Dispensing or Administration of Study Drug	X	X
Counting of Returned Study Drug		X
Initiate Subject Diary	X	

Subject Diary Review		X
Concomitant Medication Review	X	X
Adverse Experiences		

^a ±2 days

Required Components of Informed Consent

Informed consent is not a single event or just a form to be signed; it is an educational process that takes place between the investigator and the prospective subject. The basic elements of the consent process include:

full disclosure of the nature of the research and the participant's involvement, adequate comprehension on the part of the potential participant, and the participant's voluntary choice to participate.

It is the investigator's responsibility to document that the informed consent process has taken place, and an informed consent form is the standard for documenting the process for research projects involving human participants.

Consent forms must contain all the required components of informed consent as defined in SOP 9: Informed Consent Options, Processes, and Documentation and summarized below. The consent form must be written in language that is easy for a potential participant to understand and assures that individual's comprehension. Therefore, avoiding technical terms and complex sentences, even for the educated layperson, is very important.

When the participant population is not homogeneous, different consent documents may be required for different groups of people. If the research population will include participants under 18 years of age, then the IRB will expect investigators to use an assent form and a parental permission form instead (see SOP 11: Informed Consent, Enrollment, and Other Considerations for Research Involving Children). Similarly, research with cognitively or decisionally impaired individuals will require documented consent from another party—namely that person's legally authorized representative (see SOP 9, section 8 and/or SOP 10: xxx).

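### Waist circumference is not named in Appendix 1 and not taken at the early withdrawal visit, so with no missing-data method the ITT promise cannot be kept for participants who do not return for Visit 2

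*Combined protocol and SAP*

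**What the plan says.** - **Endpoint (5.1).** "The primary outcome is the relative change in WC measurement from baseline to end-of-treatment".
- **Schedule (9 and Appendix 1).** Section 9 states: "A Schedule of Events representing the required testing procedures to be performed for the duration of the study is diagrammed in Appendix 1". The appendix is headed "APPENDIX 1. EXAMPLE OF SCHEDULE OF STUDY VISITS". Its only body-size rows are height and weight. It has columns for Visits 1 and 2 and none for early withdrawal.
- **Visits (10.1 and 10.2).** The baseline list includes "12. Taking anthropometric measurements", and the end-of-study list includes "Taking anthropometric measurements". Neither names WC or hip circumference (HC).
- **Early withdrawal (10.3).** There are four items: adverse experiences and diary, concomitant medication, a complete physical examination, and finally "Perform and record vital signs".
- **Attendance (12.1 and 12.3).** Section 12.1 expects everyone who stops treatment to attend an early visit and then to be encouraged to attend the visits that remain. Section 12.3 says that those who withdraw before Visit 2 "can have an early discontinuation visit".
- **Analysis (15 and 15.1).** "The analysis of this study will include all the patients using intention to treat (ITT) methodology". The method is repeated measures ANOVA, and 15.1 puts every eligible subject in each analysis. No section says how a missing WC value is handled.

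**The concern.** Section 4.1 plans evaluations at two times only, baseline and end of study. The primary result therefore depends on one post-baseline WC per participant. If that value is not obtained, no intermediate reading can stand in for it, and 12.4 rules out replacing those who withdraw.

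The plan promises an ITT analysis but provides no WC at the one extra visit where a leaver might still be seen, and no rule for an absent Visit 2 value. What is at stake is whether the primary comparison covers everyone randomised or only those who completed. If people leave for reasons related to their response or to tolerability, and this differs between arms, the completers' comparison can be biased. Values that were never collected cannot be recovered at analysis.

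**Working it through.** **1. Is WC scheduled?** Appendix 1, described in Section 9 as the required procedures, has no WC, HC or anthropometry row. Section 10 has anthropometry at both visits. Since WC is the primary endpoint and HC a secondary one (5.1, 5.2), the natural reading is that Section 10 means to include them. The two places disagree, and neither names the endpoint.

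**2. Could another item at early withdrawal cover WC?** Section 10.1 lists the complete physical examination (item 5) separately from anthropometry (item 12), so the examination in 10.3 does not imply WC. Section 9.1.5 defines vital signs as temperature, blood pressure, pulse and respirations. As written, no WC is taken at that visit.

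**3. Who ends up without a final WC?**

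| Participant | Planned WC values | In a complete-pair ANOVA? |
|---|---|---|
| Completes | Visit 1, Visit 2 | Yes |
| Stops product, attends Visit 2 (12.1) | Visit 1, Visit 2 | Yes |
| Leaves, attends only the early visit | Visit 1 | No |
| Leaves, attends nothing further | Visit 1 | No |

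With two time points, the group-by-time test in a repeated measures ANOVA is a comparison of change scores. A participant with one value has no change score and drops out.

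**4. How many?** The documents give no dropout rate, so the rates are assumed. Number missing = 90 × rate; completers per arm = 45 × (1 − rate).

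| Assumed loss | Missing of 90 | Completers per arm | Difference detectable with 80% power (two-sided 5%, SD units) |
|---|---|---|---|
| 0% | 0 | 45 | 0.60 |
| 5% | 4.5 (about 5) | 42.75 | 0.61 |
| 10% | 9 | 40.5 | 0.63 |
| 20% | 18 | 36 | 0.67 |
| 30% | 27 | 31.5 | 0.72 |

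**5. Is power the harm?** The 17 per group in 15.6 (95% power, 5% type I error) cannot be reproduced, because no WC difference, SD or sidedness is given. It can be back-solved. By the normal approximation, d = √(2/17) × (1.960 + 1.645) = 1.24 two-sided; the t-test gives 1.28 (1.15 one-sided). Going from 17 to 45 per group allows for a loss of 1 − 17/45 = 62%. At d of about 1.27, power is 99.6% with 27 per arm (40% loss) and about 95% with 17.1 per arm (62% loss). On the plan's own implied effect, dropout does not threaten power.

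**6. What about bias?** Let p be the proportion lost in an arm and δ the mean outcome of stayers minus that of leavers. The completers' mean differs from the full-arm mean by p × δ, so the bias in the treatment difference is p₁δ₁ − p₀δ₀. With the same δ in both arms, this is δ × (p₁ − p₀). For illustration only, with δ assumed to be 3 cm, the bias is 0 if loss is equal and 3 × 0.10 = 0.3 cm if loss differs by 10 points. The documents supply neither p nor δ.

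**The case against.** The strongest reply is that much of this is already in the plan. Section 10 schedules anthropometry at both analysis times. Section 12.1 already steers those who stop treatment towards Visit 2. Appendix 1 is an unfinished template: it is headed as an example, keeps placeholder visit times, and also omits the dietary and physical-activity records listed in 10.1. Further, the analysis concerns WC after 12 weeks, so a reading at early withdrawal is not the endpoint value, and adding it would not by itself deliver ITT. All of this stands, and it rules out four stronger readings that a reader might infer:

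- **That WC is not collected at all.** Section 10 does not support this. The endpoint is unnamed, not unscheduled.
- **That anyone who stops early lacks a final WC.** Section 12.1 gives those who stop product a route to Visit 2. The gap is certain only for those who do not return.
- **That the trial becomes underpowered.** The margin of 45 over 17 per group covers this on the plan's implied effect. If the true effect were nearer 0.6 SD, loss would cost some sensitivity, as the table shows, but the plan was not sized for that effect.
- **That only one WC reading is taken.** The number of readings is not stated, so no gain from duplicate readings can be worked out from the documents.

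The objection does not supply a WC at early withdrawal, agreement between 12.1 and 12.3 on attendance, or a method for absent Visit 2 values.

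**Conclusion.** The point holds in limited form. WC is missing by name from the schedule that Section 9 calls required, and anthropometry is absent from the early withdrawal visit. Sections 12.1 and 12.3 conflict on whether that visit is expected. Participants who leave and do not return for Visit 2 would have a baseline WC only, and the stated ANOVA, run on complete pairs, would exclude them, contrary to Sections 15 and 15.1.

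The main harm is possible bias from selective loss. Its size is unknown. The 5-27 missing of 90 rests on an assumed 5-30% loss, and the 0-0.3 cm illustration rests on an assumed 3 cm difference between stayers and leavers and a loss imbalance of 0-10 points. If nearly everyone attends Visit 2, the effect on the result is negligible. The change is still worth making, because it is cheap and determines which data exist for the primary analysis. The missing rows in Appendix 1 are mainly a matter of clarification.

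**What to change.** 1. **Appendix 1 and Section 10.** Name WC and HC at Visit 1 and Visit 2 in both places so that they agree. Add an early withdrawal column to Appendix 1 with the same two measurements.
2. **Section 10.3.** Add WC and HC to the early withdrawal visit.
3. **Section 12.3.** Align it with 12.1, so that everyone who stops product is asked to return for WC at the Visit 2 date. Participants remain free to decline.
4. **Section 15.** Because an early WC is not a 12-week value, pre-specify an analysis that keeps all randomised participants. One example is multiple imputation of the Visit 2 WC from baseline and early-withdrawal WC, by arm, with a sensitivity analysis that lets leavers differ from stayers. Report the number missing and the reasons by arm.

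The cost is a tape measurement of a few minutes at visits already planned, some wording, and a little more analysis work. Duplicate readings at a fixed landmark would be an optional refinement.
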